Project proposal for the PhD project:

Psychiatric comorbidity in Back Pain Disorders
– Risk, treatment and pharmaco-epidemiological analysis

Applicant

[name], MscPH

Medical Research Department, Spine Centre of Southern Denmark

Last update: 29 of January 2019

Introduction

Chronic pain is a common health problem negatively affecting sleep, work ability and socialization¹⁻⁴. Chronic pain also increases morbidity, mortality and health care costs and has a direct and severe impact on the quality of life^{3 5-8}. The prevalence of chronic pain is up to 46,5% in the general population⁵. Musculoskeletal back and neck pain are one of the most common pain conditions^{2 9} with a lifetime prevalence of low back pain in the range of 51%-84%⁶. Variation in prevalence estimates can be explained by a difference in the definition of pain, research methodologies and differences in study samples¹⁰.

Several different diagnostic classifications systems for back pain disorders (BPD) exist, but most frequently these are divided into specific and non-specific BPD¹¹. This study chooses to establish two subgroups for specific BPD based on the presumed cause of illness and available treatment options and one group for unspecified BPD (UBD). The specific subgroups consists of inflammatory back diseases (IBD) and degenerative back diseases (DBD)¹².

Clinical guidelines recommend that treatment consists of a combination of medical, surgical and non-pharmacological interventions such as patient education, physical- and occupational therapy, cognitive-behavioral therapy, nutritional counseling and self-management strategies¹³⁻¹⁶. The most frequent treatment of BPD is pharmacological¹⁷. Despite not being generally recommended for treatment of back pain disorders¹⁸, opioids are prescribed in up to 66% of patients¹⁹. The prevalence of concomitant substance abuse disorder in BPD patients receiving opioid treatment is up to 43%¹⁹. Previous studies fail to establish, which type of back pain patients are prescribed opioids and which specific other psychiatric comorbidities than substance abuse are linked to higher opioid consumption. It does seem, that patients with a high burden of psychiatric comorbidity, have a higher rate of opioid misuse, although studies are old, small and heterogeneous²⁰⁻²³. Several studies on the association between back pain and psychiatric disorders, focusing on depression and anxiety disorders, have been conducted. However, these studies have several limitations: they do not include other types of psychiatric comorbidity²⁴⁻²⁹ and they are often based on questionnaires. Including nationwide data sources might minimize potential selection bias. Furthermore, many studies have focused on large heterogeneous groups of patients with nonspecific back pain symptoms instead of being based on BPD diagnosis as defined by the ICD-10³⁰. The majority of studies do not compare different BPD-diagnosis when assessing psychiatric comorbidity.^{24 27 31-33}

To more accurately assess the risk of psychiatric comorbidity in patients with back pain disorders, population-based registry data could be utilized. The Danish health registries are generally considered to have a high validity, however there are limitations to consider, as described in previous studies on each registry^{34 35 36 37}, which has to be taken into consideration when interpreting results based on data from these registries.

When investigating psychiatric comorbidity in BPD patients, focusing on anxiety and depression, has been the norm. However, important information on the relationship between other types of mental illness and back pain disorders might be identified, if a dataset of sufficient size and quality, is used for analysis. A population-based set of registry data as the ones available in Denmark provides this. By grouping psychiatry comorbidity according to ICD-10, mental illnesses with common pathways are analyzed together. In the ICD-10 system psychiatric diagnosis are grouped according to symptomatology and common etiology³⁰. All psychiatric diagnoses are considered relevant in the chosen population, as any psychiatric disorders represents a vulnerable patient with possible complicating factors when treating back pain. The limitation of Danish registry-based data is, that it does not provide complete data from the primary care sector selecting only severe psychiatric diagnosis. In conclusion, back pain disorders and the association with psychiatric comorbidity has primarily been investigated using symptomatology, not ICD-10 diagnoses and with a focus on anxiety and depression. The studies are small, heterogeneous and of varying quality. The use of pharmacological treatment, including opioids, in back pain disorders complicated by psychiatric comorbidity is unknown.

Aim of the thesis

The aim of this PhD thesis is to use population-based registry data to:

1) to estimate the prevalence of psychiatric comorbidity in patients with back pain disorders (BPD) compared to patients with no back pain in the time period 2010-2014; 2) Investigate whether presence of psychiatric comorbidity affects utilization of pharmacological, surgical and other types of treatment for patients with BPD 3) Investigate whether presence of psychiatric comorbidity affects utilization and dosages of pharmacological treatment for patients with BPD.

Clinical contributions of this PhD

This PhD study will contribute with new knowledge on the association between different types of BPD and psychiatric comorbidity. As BPD affects a large part of the population, this is a very important area of research from a public health and clinical perspective. Access to nationwide registries facilitates a comprehensive and population-based dataset, ensuring the ideal circumstances for investigating the association between BPD and potential psychiatric comorbidity. Furthermore, the results can be used to increase clinical awareness of vulnerable patients in the intersection between rheumatology and psychiatry and subsequently improve prevention and clinical management for a complex and resource-demanding patient population.

Materials and methods

Setting and study population

This PhD project includes a population-based nationwide cohort based on data from Danish health registries. Danish health registries, including The Danish National Patient Registry (DNPR), a subdivision of the DNPR, the National Patient Registry – Psychiatry (NPD-Psych), The Danish National Prescription Database and The Danish National Health Service Register, contains complete data on hospital contacts, prescription drug use and services provided by health contractors. By using the Danish Civil Registry and the unique personal identification number assigned to all Danish citizens at birth, data across registries can be linked on an individual level^{34 35 36 37}.

The study population will be defined as all adult patients (18+) identified in the DNPR³⁴, covering all inpatient and outpatient services in Denmark, in the time period 1th of January 2010 to 31th of December 2014 with a diagnosis of BPD according to the ICD-10 Classification of Disease (DM*).³⁰

Psychiatric comorbidity will be defined as the presence of any of the following diagnosis, according to ICD-10 classification³⁰, obtained from the National Patient Registry – Psychiatry (NPD-Psych), covering all inpatient and outpatient psychiatric services in Denmark in the time period 1th January 2007 to 31th December 2017: Organic, including symptomatic, mental disorders (F00-DF09), Mental and behavioral disorders due to psychoactive substance use (F10-F19), Schizophrenia, schizotypal and delusional disorders (F20-F29), Mood [affective] disorders (F30-F39), Neurotic, stress-related and somatoform disorders (F40-F48), Behavioral syndromes associated with physiological disturbances and physical factors (F50-F59), Disorders of adult personality and behavior (F60-F69), Mental retardation (F70-F79), Disorders of psychological development (F80-F89), Behavioral and emotional disorders with onset usually occurring in childhood and adolescence (F90-F98) and, Unspecified mental disorder (F99). To qualify as a psychiatric comorbidity to back pain disorder, we define that the psychiatric diagnosis must be given no earlier than three years prior to back pain disorder diagnosis and no later than three years after.

Study 1) Prevalence of psychiatric comorbidity in back pain disorders

Psychiatric comorbidity in Back Pain Disorders
Risk, treatment and pharmaco-epidemiological analysis

Aim: 1) To estimate prevalence of psychiatric comorbidity in patients with BPD compared to patients without BPD and 2) To estimate prevalence of psychiatric comorbidity in patients with unspecific back pain (UBP) compared to the background population and to patients with a specific back pain (SBP) in a Danish nationwide cohort from 2010-2014.

Hypothesis: 1) There is a higher risk of psychiatric comorbidity in BPD patients compared to the background population and 2) UBP patients have a higher risk of psychiatric comorbidity compared to patients with specific BPD.

Design: The study will be a nationwide register-based matched cohort study.

Procedure: Selected BPD patients with the following diagnosis will be identified via the DNPR: Spondylopathies DM45-49, Other dorsopathies DM 50-54 and Segmental and somatic dysfunction DM99. Each patient will be matched 1:5 on age and sex with patients without back disorders by random at Statistics Denmark³⁸. The selection of diagnosis is to be able to match the population with non-BPD patients in the Danish registries.

Information on somatic comorbidity for calculation of Charlson Comorbidity index³⁹ (CCI) at time of BPD diagnosis, will be retrieved from the DNPR. Data on psychiatric comorbidity will be identified using NPD-Psych. Information on marital status, vital status, and immigration status will be retrieved from the Civil Registration System (CPR)³⁵. Patients that are not alive or have emigrated within three years after BPD diagnosis are considered lost to follow-up and excluded from the cohort. Descriptive data on the socioeconomic status, education level and equivalent available income will be retrieved from Statistics Denmark³⁸. All data comprising each variable will be retrieved from 1th of January 2007 to 31th of December 2017 (three years before and after study period).

Measures of outcome: Primary outcome is to estimate prevalence of psychiatric comorbidity in patients with BPD compared to the Danish background population. Secondary outcome is to estimate prevalence of psychiatric comorbidity stratified by type of BPD (SBP UBP) compared to the Danish background population. We will use a presence of psychiatric comorbidity as outcome.

Statistics: We will use Fisher's exact test and t-test to compare baseline characteristics with 95% confidence intervals (CI) and p-values. Crude risks of psychiatric comorbidity will be calculated and logistic regression model will be used, to investigate differences between the distribution of risk in BPD patients and the background population. A logistic regression model will also be used to investigate differences between the distribution of psychiatric comorbidity in the IBD, DBD and UBP group compared to the background population. The logistic regressions will be reported using 95% CI and adjusted for the following confounders: age, sex, equivalent available income, educational level, CCI, marital status.

Study 2) The effect of psychiatric comorbidity on type of treatment for BPD

Aim: 1) To investigate whether treatment of BPD in patients with psychiatric comorbidity differ from treatment of patients with BPD without psychiatric comorbidity; 2) To investigate whether treatment of BPD differs in the following subgroups: a) specific BPD and no psychiatric comorbidity; b) specific BPD with psychiatric comorbidity; c) unspecific BPD with no psychiatric comorbidity; d) unspecific BPD with psychiatric comorbidity. Investigation will be performed in a nationwide Danish cohort in 2010-2014.

Hypothesis: 1) Psychiatric comorbidity affects type of treatment in BPD patients and 2) psychiatric comorbidity affects type of treatment in subgroups of BPD.

Design and study population: The study will be a nationwide register-based cohort study. The study population consists of patients with BPD and in the sub-analysis the study population consists of patients with BPD and psychiatric comorbidity.

Procedure: BPD patients will be identified via the DNPR. Surgical treatment will be defined as the presence of any procedure code for back surgery retrieved from DNPR (NOMESCO: KNA-W)³⁴⁻⁴⁰. Pharmacological treatment of BPD will be defined as any treatment with the following drugs: NSAID (ATC: N01A*), acitomenophen (ATC: N02BE01), opioids (N02A*), antiepileptica (ATC: N03A) and tricyclic antidepressants (ATC: N06AA)¹³ identified using the Register of Medicinal Products Statistics⁷. Data on other types of treatment (defined as any treatment not surgical or pharmacological) such as physiotherapist, psychologist, chiropractor or occupational therapist (covered via tax-funded health insurance) will be obtained via The Danish National Health Insurance Service Register (SSR)³⁷. All BPD treatment-related information will be retrieved up to three years after the date of BPD diagnosis.

Information on somatic comorbidity for calculation of Charlson Comorbidity index³⁹ (CCI) at time of BPD diagnosis, will be retrieved from the DNPR. Data on psychiatric comorbidity will be identified using NPD-Psych. Information on psychiatric comorbidity will be used to define whether each patient had a psychiatric diagnosis prior to BPD diagnosis, after BPD diagnosis or no psychiatric diagnosis. If a psychiatric diagnosis occurs both prior to and after BPD diagnosis, the patient will be defined as having a psychiatric comorbidity prior to BPD diagnosis.

Information on marital status, vital status, and immigration status will be retrieved from the Civil Registration System (CPR)³⁵. Patients that are not alive or have emigrated within three years after BPD diagnosis are considered lost to follow-up and excluded from the cohort. Descriptive data on the socioeconomic status, education level and equivalent available income will be retrieved from Statistics Denmark³⁸. All data comprising each variable will be retrieved from 1th of January 2007 to 31th of December 2017 (three years before and after study period).

Measures of outcome: The outcome is type of treatment for BPD (surgical, pharmacological and other types of treatment)

Statistics: We will use Fisher's exact test and t-test to compare patients' baseline characteristics with 95% confidence intervals (CI) and p-values. For each treatment type we will use logistic regression model to investigate differences in outcome distribution between patients with and without psychiatric comorbidity. The logistic regressions will be performed with 95% CI adjusted for the following confounders: age, sex, CCI, level of education, equivalent available income, type of BPD (IBD, DBD or UBP) and marital status.

Study 3) Effect of psychiatric comorbidity in pharmacological treatment of BPD.

Aim: 1) To compare dosages of pharmacological treatment in BPD patients with and without the presence of psychiatric comorbidity in a nationwide Danish cohort study in 2010-2014. 2) To compare high vs. low dosages of pharmacological treatment for BPD in patients with BPD and psychiatric comorbidity.

Hypothesis: 1) Patients with BPD and psychiatric comorbidity are prescribed a higher dosage of pain medication for BPD compared with BPD patients without psychiatric comorbidity. 2) BPD patients with a psychiatric comorbidity with a high (defined as above the 50th percentile) vs. low (defined as below the 50th percentile) dosage of pain medication are also prescribed higher dosages of psychiatric medication.

Design and study population: The study will be a nationwide register-based cohort study. The study population consists of patients with BPD that received pharmacological treatment for BPD. In the secondary analysis the study population consists of patients with BPD and a psychiatric comorbidity, who received pharmacological treatment for BPD.

Procedure: BPD patients will be identified via the DNPR. Pharmacological treatment of BPD will be defined as any treatment with the following drugs: NSAID (ATC: N01A*), Acitomenophen (ATC: N02BE01), Opioids (N02A*)¹³. Pharmacological treatment for psychiatric comorbidity will be defined as any treatment with the following drugs: Antipsychotics (ATC:N05A), Antidepressants (ATC: N06A), Selective Serotonin Reuptake Inhibitors (SSRI) (ATC: N06AB), and anxiolytics (ATC: N5B*)⁴¹. Pharmacological treatment that can be used in the treatment of both BPD and psychiatric disorders will be defined as any treatment with the following drugs: Antiepileptics (ATC: N03A) and Tricyclic antidepressants (ATC: N06AA). All data on pharmacological treatment will be identified using the Register of Medicinal Products Statistics⁷. From time of BPD diagnosis and the following three years, pharmacological treatment for both somatic illness and psychiatric comorbidity in Daily Defined Dosage (DDD) per year will be calculated⁴².

Information on somatic comorbidity for calculation of Charlson Comorbidity index³⁹ (CCI) at time of BPD diagnosis, will be retrieved from the DNPR. Data on psychiatric comorbidity will be identified using NPD-Psych. Information on marital status, vital status, and immigration status will be retrieved from the Civil Registration System (CPR)³⁵. Patients that are not alive or have emigrated within three years after BPD diagnosis are considered lost to follow-up and excluded from the cohort. Descriptive data on the socioeconomic status, education level and equivalent available income will be retrieved from Statistics Denmark³⁸. All data comprising each variable will be retrieved from 1th of January 2007 to 31th of December 2017 (three years before and after study period).

Measures of outcome: Primary outcome is pharmacological treatment in DDDs defined as high (above the 50th percentile and low (below the 50th percentile) of pain medication. Secondary outcome is psychiatric medication in BPD patients with psychiatric comorbidity in DDD's defined according to high (above the 50th percentile) and low (below the 50th percentile) dosages of pain medication.

Statistics: We will use Fisher's exact test and t-test to compare patients' baseline characteristics with 95% confidence intervals (CI) and p-values. Time dependent Cox regression will be performed separately for patients with specific and unspecific BPD to examine dosage of pharmacological treatment over time comparing patients with and without psychiatric comorbidity. The analysis will be performed with 95% CI and adjusted for the following confounders: age, sex, CCI, level of education, equivalent available income, marital status and the presence of psychopharmacological treatment.

To examine dosage of psychopharmacological treatment over time comparing patients with psychiatric comorbidity and low vs high dose of pharmacological treatment of BPD, time dependent Cox regression will be performed reporting 95% CI and adjusting for the following confounders: age, sex, CCI, level of education, equivalent available income, marital status.

Psychiatric comorbidity in Back Pain Disorders
Risk, treatment and pharmaco-epidemiological analysis

Ethics

All studies will be based on national clinical registries and approval is obtained by The Danish Health Data Board and the Danish Data Protection Agency (18/3337). According to Danish law, further ethical approval is not required for purely registry-based studies. All data will be stored on Statistics Denmark's servers and will be anonymized ensuring no patients can be identified.

PhD Outline

The PhD will be conducted within a timeframe of three years (six semesters).

	1st semester	2nd semester	3rd semester	4th semester	5th semester	6th semester
Data collection	X					
PhD Courses	X	X	X			
Data analysis		X	X	X	X	
Writing articles			X	X	X	X

References

1. Hawker GA. The assessment of musculoskeletal pain. *Clinical and experimental rheumatology* 2017;35 Suppl 107(5):8-12.

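### With no index-date or washout rule, patients first coded with BPD before 2010 can enter mid-course, which shifts the comorbidity window and treatment period in Studies 2 and 3

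*Combined protocol and SAP*

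**What the plan says.** - **Entry** (Setting and study population): adults in the DNPR "in the time period 1th of January 2010 to 31th of December 2014 with a diagnosis of BPD". The text does not restrict this to a new or first diagnosis.
- **Case finding** (Study 2, Procedure): "BPD patients will be identified via the DNPR. Surgical treatment will be defined as the presence of any procedure code for back surgery". Neither this section nor the matching one in Study 3 excludes people with earlier BPD codes or names the contact that counts as the BPD date.
- **Comorbidity window** (Setting and study population): the psychiatric diagnosis "must be given no earlier than three years prior to back pain disorder diagnosis and no later than three years after".
- **Timing label** (Study 2, Procedure, only): psychiatric data will show "whether each patient had a psychiatric diagnosis prior to BPD diagnosis, after BPD diagnosis or no psychiatric diagnosis". If there are diagnoses on both sides, "the patient will be defined as having a psychiatric comorbidity prior to BPD diagnosis".
- **Follow-up**: Study 2 collects treatment until three years after the BPD date. Study 3 computes DDDs per year over the three years that begin at that date.
- **Data window** (all three studies): "All data comprising each variable will be retrieved from 1th of January 2007 to 31th of December 2017". The stated uses of data from before the BPD date are psychiatric diagnoses and the Charlson index, for which information "at time of BPD diagnosis, will be retrieved from the DNPR".

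**The concern.** One date carries most of the design. It sets the comorbidity window, the timing label in Study 2, the treatment period in Study 2, the DDD period in Study 3 and the exclusion for death or emigration. The plan does not define that date beyond a BPD code falling in 2010–2014.

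Take a patient first coded in 2008 and seen again in 2011. Under the text as written, the BPD date is 2011. Surgery in 2009 is not counted as an outcome. Drug use is measured from the third year of the disease. A depression diagnosed in 2009 is filed as *prior* to BPD.

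The models in Studies 2 and 3 adjust for neither BPD duration nor earlier BPD contacts, so they cannot separate such patients from new ones. If patients with psychiatric illness return to hospital for back pain more often, the mixture would also differ between the groups compared. The documents give no evidence on that, so it is a possibility and not a finding.

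**Working it through.** **1. Is a lookback feasible?** Retrieval starts on 1 January 2007. A patient entering on 1 January 2010 has 3.0 years of lookback, and one entering on 31 December 2014 has 8.0 years. A washout is possible for every entrant, provided that the extract includes BPD codes from before 2010.

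**2. Where does a late date act?**
- *Study 2 label:* the error runs one way. A date that is too late turns *after* into *prior*, and the rule for diagnoses on both sides adds to this.
- *Study 2 model:* the stated contrast is comorbidity present versus absent. Relabelling leaves the patient comorbid. The estimate is affected through the displaced window and the displaced treatment period.
- *Study 3 models:* no timing label exists. The effects are a displaced time origin and window.

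**3. Size of the label error (illustration).** The plan gives no figure to reproduce. Assume that a share f of the cohort is prevalent, that their true first BPD diagnosis lies L years before the recorded date (L ≤ 3), and that each comorbid patient has one psychiatric date, uniform over the six-year window. Then f·L/6 of comorbid patients, or f·L/3 of those labelled *prior*, are labelled wrongly.
- f = 30%, L = 1: 0.30 × 1/6 = 5%, and 0.30 × 1/3 = 10%.
- f = 30%, L = 2: 10% and 20%.
- f from 10% to 50% with L from 0.5 to 3: 0.8% to 25%, and 1.7% to 50%.

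The same f·L/6 is the share of counted comorbid patients whose psychiatric date lies outside the window around the true first diagnosis. That part does reach the present-versus-absent contrast.

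**4. Prevalent share and the effect of a washout (illustration).** Assume constant onset from 2000 to the end of 2014, a code at onset, and Poisson re-contacts at yearly rate r. Neither input is in the documents. In units of one year's onsets:
- New patients: 5.
- Prevalent patients with a code in 2010–2014: P = 10(1 − e^(−5r)). Their share is P/(5 + P).
- Still included after excluding any code from 2007 up to the index date: K₁ = 7e^(−3r)(1 − e^(−5r)).
- Still included after a uniform three-year washout before the first code in 2010–2014: K₂ = 25.5·r·e^(−3r) + 10(e^(−3r) − e^(−5r)), where 25.5 is the integral of (7 + t) from 0 to 3.
- Prevalent share afterwards: K/(5 + K). Patients lost: (P − K)/(5 + P).

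| r | P | No rule | K₁ | 2007 rule: share (lost) | K₂ | Three-year rule: share (lost) |
|---|---|---|---|---|---|---|
| 2% | 0.952 | 16% | 0.627 | 11% (5%) | 0.850 | 15% (2%) |
| 5% | 2.212 | 31% | 1.333 | 21% (12%) | 1.917 | 28% (4%) |
| 10% | 3.935 | 44% | 2.040 | 29% (21%) | 3.232 | 39% (8%) |

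Example, r = 5%: 2.212/7.212 = 31%; 1.333/6.333 = 21%; (2.212 − 1.333)/7.212 = 12%.

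If a patient who fails the three-year rule may re-enter at a later qualifying code, a simulation of 400,000 patients puts the last share at about 40%, with about 7% lost. On these assumptions the uniform washout removes much less than the rule reaching back to 2007.

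**The case against.** The strongest reply is that the aims concern treatment of people with BPD, not of newly diagnosed people. Established hospital patients belong to that target, and a washout in Studies 2 and 3 would change the question. This stands as a reason to allow a sensitivity analysis in place of an exclusion. It does not excuse leaving the index date undefined, because the windows and follow-up depend on it under either target.

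Four further limits stand:
- A reader might infer that Study 3 also misclassifies *prior* versus *after*. It defines no such variable.
- A reader might infer that the label error biases the main Study 2 estimate. The stated model does not use the label.
- A reader might take the 2007–2009 BPD codes as already in hand. The retrieval sentence covers all variables from 2007, which implies this, but no text says that BPD codes before 2010 are extracted.
- The re-contact rates and the onset date of 2000 are assumptions, and they drive the percentages.

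Study 2 also gives the end of its treatment window without spelling out its start. Starting at the BPD date is the natural reading, and Study 3 says so outright. The claim that earlier surgery is missed rests on that reading.

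**Conclusion.** The point holds as a gap in the design that should be closed before analysis. The plan admits any BPD code in 2010–2014 without an index-date or washout rule, so patients can enter mid-course. In Studies 2 and 3 this displaces the comorbidity window and the treatment or DDD period, and no planned covariate corrects for it. In Study 2 the *prior* label can also be wrong, which matters only where it is analysed.

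The documents show that this can happen, not how often. The prevalent shares of 16% to 44% describe assumed scenarios and should not be read as estimates for this cohort. Nor do the documents support calling Study 1 wrong on this ground: it targets prevalence, so including prevalent BPD is not in itself an error there.

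**What to change.** 1. Define the index date as the first listed BPD code in 2010–2014.
2. In Studies 2 and 3, exclude patients with any listed BPD code from 1 January 2007 up to the index date. If the target is to remain all hospital BPD patients, keep them and prespecify this incident-only cohort as a sensitivity analysis.
3. Leave Study 1 unchanged, with the same sensitivity analysis.
4. Confirm that the DNPR extract includes BPD codes for 2007–2009.

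The cost is an eligibility sentence and a filter, if the codes are in the extract. Under the illustrative assumptions, Studies 2 and 3 lose about 5% to 21% of patients. The lookback varies from 3 to 8 years with entry date. A uniform three-year washout would equalise it but removes less. Either rule is partial, because back pain last coded before the lookback, or seen only in primary care, stays undetected.

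### Study 3 pools substance use disorders (F10-F19), including those diagnosed after the back pain diagnosis, with all other psychiatric disorders in one yes/no exposure, so a higher pain-drug dosage could partly reflect reverse causation or a link the plan already treats as known

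*Combined protocol and SAP*

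**What the plan says.** The exposure is defined for all three studies under Materials and methods, Setting and study population: "Psychiatric comorbidity will be defined as the presence of any of the following diagnosis". The list that follows covers the whole ICD-10 psychiatric chapter and names "Mental and behavioral disorders due to psychoactive substance use (F10-F19". A diagnosis qualifies if given "no earlier than three years prior to back pain disorder diagnosis and no later than three years after".

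In Study 3, hypothesis 1 is that "Patients with BPD and psychiatric comorbidity are prescribed a higher dosage of pain medication for BPD compared with BPD patients without psychiatric comorbidity". The Procedure defines pain medication as "NSAID (ATC: N01A*), Acitomenophen (ATC: N02BE01), Opioids (N02A", followed by a wildcard. The measurement period is stated thus: "From time of BPD diagnosis and the following three years, pharmacological treatment for both somatic illness and psychiatric comorbidity in Daily Defined Dosage (DDD", expressed per year. The primary outcome splits this dosage at the median. The Statistics paragraph plans a time-dependent Cox regression, run separately for specific and unspecific BPD, that contrasts patients who have psychiatric comorbidity with those who do not. It gives no estimate by ICD-10 block and no split by timing of diagnosis.

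The Introduction states that "The prevalence of concomitant substance abuse disorder in BPD patients receiving opioid treatment is up to 43" per cent, and that earlier studies do not establish "which specific other psychiatric comorbidities than substance abuse are linked to higher opioid consumption".

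**The concern.** Substance use disorder differs from the other blocks in this exposure because it can arise from one of the drug classes that make up the outcome. Suppose a patient is prescribed opioids heavily in the first year after the BPD diagnosis and receives an opioid-related F10-F19 diagnosis in the second. That patient enters Study 3 as exposed and counts in favour of hypothesis 1, although the order of events runs from dosage to diagnosis.

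Even without reverse causation, the pooled contrast mixes a link that the Introduction regards as known with one that it regards as open. The third thesis aim asks whether comorbidity affects dosages. A positive result could be read as showing that mood, anxiety, psychotic and other disorders go with higher dosage when the signal comes from F10-F19 alone.

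**Working it through.** The plan gives no effect size, sample size or expected prevalence for Study 3, so there is no figure of its own to reproduce. The check sets the definitions side by side and then illustrates what could follow.

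**1. Windows.** Exposure runs from -3 to +3 years around the BPD diagnosis and outcome from 0 to +3 years. The second half of the exposure window is the whole outcome window.

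**2. Safeguards in Study 3.**
- The adjustment set for the main model is age, sex, Charlson index, education, income, marital status and presence of psychopharmacological treatment. It has no term for substance use disorder or for opioid use before baseline.
- The classification of psychiatric diagnoses as before or after BPD appears only in the Study 2 Procedure.
- The Introduction mentions grouping by ICD-10, but no Statistics paragraph turns this into estimates by block.

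**3. Illustration of pooling (all inputs assumed).** Let 50% of patients without comorbidity have high dosage, let other disorders have no association (OR 1.0), and let F10-F19 have OR 3 or 4, so that P(high) is 0.75 or 0.80. With F10-F19 making up a share s of the comorbid group, pooled P = 0.5 + s × (0.25 or 0.30).
- s = 10%: P = 0.525 or 0.530; OR = 0.525/0.475 = 1.11 or 0.530/0.470 = 1.13.
- s = 25%: P = 0.5625 or 0.575; OR = 0.5625/0.4375 = 1.29 or 0.575/0.425 = 1.35.

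This shows dilution of a subgroup association, not reverse causation.

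**4. Illustration of reverse causation (all inputs assumed).** Let other disorders have prevalence q in both dosage halves, so that they are unrelated to dosage. Let F10-F19 arise independently of them with risk f in the low half and k × f in the high half. Then P(any comorbidity) = 1 - (1 - q)(1 - F10-F19 risk).
- Middle scenario, q = 10%, f = 2%, k = 3. High half: 1 - 0.90 × 0.94 = 0.154. Low half: 1 - 0.90 × 0.98 = 0.118. OR = (0.154/0.846)/(0.118/0.882) = 1.36.
- Lowest, q = 20%, f = 1%, k = 2: 0.216 against 0.208, OR 1.05.
- Highest, q = 5%, f = 5%, k = 5: 0.2875 against 0.0975, OR 3.74.
- With k = 1 (no reverse effect) the OR is 1.00.

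**5. Why a split must use diagnoses made before BPD.** Keep the setting of step 4, but let patients with other disorders have twice the F10-F19 risk (assumed). If patients are sorted by F10-F19 diagnoses made during follow-up, the contrast of psychiatric diagnosis without F10-F19 against none becomes OR = [(1 - 2kf)/(1 - 2f)] × [(1 - f)/(1 - kf)].
- f = 1%, k = 2: (0.96/0.98) × (0.99/0.98) = 0.99.
- f = 5%, k = 5: (0.50/0.90) × (0.95/0.75) = 0.70.

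The true value is 1.00. Sorting on later diagnoses removes high-dosage patients unevenly and creates a bias of its own.

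**The case against.** Including every psychiatric diagnosis is deliberate. The Introduction argues that any such disorder marks a vulnerable patient, and both the third aim and hypothesis 1 concern psychiatric comorbidity as a whole. The pooled contrast answers that question. This stands, and it is why that contrast should remain the plan's test of hypothesis 1.

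A reader might infer that Study 3 fails its stated purpose because it does not isolate disorders other than substance abuse. The documents do not support that. The sentence on other comorbidities is literature background, not an aim, and the Introduction closes on a wider gap, the unknown use of pharmacological treatment in BPD with psychiatric comorbidity, which Study 3 does address.

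A reader might also infer that the outcome defines the exposure. That is too strong. F10-F19 covers all psychoactive substances, and only disorders arising from the study drugs can be circular. The outcome also pools opioids with the codes labelled NSAID and acetaminophen, which dilutes any effect.

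The overlap of windows affects every psychiatric block, so timing is part of the problem and a split by block alone would not solve it. A time-dependent Cox model could treat comorbidity as time-varying and so order some events, but the plan does not say that it will. Ordering would neither separate F10-F19 from other disorders nor remove diagnoses caused by earlier opioid use.

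**Conclusion.** The point holds in a limited form. As planned, a higher dosage in the comorbid group could partly reflect reverse causation through F10-F19 or the already described substance-abuse link, and the single contrast cannot show whether other disorders are linked to dosage.

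The size is not derivable from the documents. The odds ratios above rest entirely on assumed shares, risks and effects, and they use the median split rather than the planned Cox model. They show what could happen, not what will. The reported ceiling of 43% must not be used as a share: it describes substance abuse among opioid-treated BPD patients, not the proportion of the comorbid group with F10-F19. Nor do the documents support moving the test of hypothesis 1 to patients without F10-F19. That would replace the plan's question and, if patients were sorted on diagnoses made during follow-up, could bias the estimate downwards.

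**What to change.** Keep the all-diagnosis contrast for hypothesis 1. In the Study 3 Statistics paragraph, pre-specify beside it:

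- A three-level exposure: no psychiatric diagnosis; any F10-F19, with or without others; psychiatric diagnosis without F10-F19. Classify it on diagnoses given before the BPD diagnosis, carrying over the before/after classification from Study 2 and applying it by block.
- A rule that no patient leaves a comparison group because of an F10-F19 diagnosis made during follow-up. Each patient stays in the level that the history before BPD gives.
- A reporting rule: present the F10-F19 level as an association without direction, and conclude that comorbidity other than substance use is linked to dosage only if the contrast without F10-F19 supports it.
- A sensitivity analysis for hypothesis 2 that omits patients with F10-F19 before BPD.

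The diagnoses are already being retrieved, so the work is a short text change and a few more model runs. The exposed groups become smaller and the intervals wider, by an amount that cannot be stated because the plan gives no sample size. Some reverse causation from opioid use before the BPD diagnosis would remain and should be named as a limitation.
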